5 RESEARCH QUESTION AND OBJECTIVES

The overall research questions for this study are:

1. What are the demographic, clinical, and treatment characteristics of a population of patients who initiate inebilizumab in real-world practice?
2. What are inebilizumab patterns in the first 12 months following treatment initiation?
3. What is the incidence of adverse events of special interest (AESI) in the first 12 months following treatment initiation?

Specific objectives are:

1. To describe patients at time of first inebilizumab treatment – in the overall study population and in sub-groups of special interest (patients concomitantly receiving other immunosuppressive agents and patients aged >65 years at index date) – in terms of:
 - demographics
 - comorbidities
 - NMOSD-related clinical characteristics
 - previous immunosuppressive therapies
 - inebilizumab initiation characteristics (setting of healthcare and specialty of prescribers and treatment indication)
2. To describe inebilizumab treatment patterns in the overall study population and sub-groups of special interest in the first 12 months after starting treatment - in terms of:
 - duration of treatment
 - dosing
 - frequency of drug discontinuation
 - switching
 - use of add-on therapies
3. To quantify the incidence of AESI in the overall study population and sub-groups of special interest, including:
 - serious infections
 - opportunistic infections (including progressive multifocal leukoencephalopathy [PML])
 - hepatitis B reactivations
 - serious infusion related reactions
 - malignancies

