6 RESEARCH METHODS

6.1 Study Design

This will be a non-interventional multi-center cohort study of patients initiating inebilizumab conducted with secondary data sources in France, Germany, Italy, the Netherlands, and Spain. The study will be based on a cohort-event monitoring design to capture both drug utilization and selected safety outcomes in patients initiating inebilizumab. The proposed study design allows for an efficient initial descriptive evaluation of AESI.

The **study period** in individual countries will start on different dates, depending on the launching time of the drug (the earliest in the second quarter of 2022) (Table 1). The end of the study period will be also country-specific (the latest in December 2027) and will depend on the dates of data availability in individual data sources (different lag times and data release dates).

Table 1 Study periods, by country

	France	Germany	Italy	Netherlands	Spain
	SNDS/ NOMADMUS	GKV	RISM	PHARMO	SIDIAP
Launch date (quarter, year)	Q2, 2022	Q3, 2022	Q2 2023	Q3, 2023	Q2, 2023
Start of study period	May 2022	Aug 2022	May 2023	Aug 2023	May 2023
End of study period	Dec 2026	Dec 2026	Dec 2027	Dec 2026	Sep 2027
Study period duration (months)	57	54	56	41	53

Q2, 2nd quartile; Q3, 3rd quartile

The study population will be constituted by a cohort of adult female and male patients diagnosed with NMOSD with entry trigger by inebilizumab initiation.

[figure not shown]
The **index date** (Day 0) will be defined as the date of first treatment (date of administration/prescription/dispensation, depending on data available in selected data sources) (Figure 1). Patients initiating the treatment will be identified throughout the study period. After the index date, enrolled patients will be followed for 12 months or censored at end of study period or loss of follow-up (death, disenrollment/de-registering) whichever occurs first.

A **baseline period**, including any time from when data are available up to the index date, will be used to establish comorbidities and NMOSD-related clinical characteristics, whereas a short period of 6 months prior to or at index date will be used to determine previous immunosuppressive therapies.

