6.3.3 Treatment patterns

During follow-up, treatment patterns will be characterized in terms of dose, treatment duration, frequency of drug discontinuation, switching and use of add-on therapies. All patients included in the study will be deemed exposed (at least one inebilizumab treatment), but only those with complete 12-month follow-up will be considered in the evaluation of the treatment patterns as described below.

According to the product specifications, the 12-month follow-up will cover 3 potential inebilizumab administrations: initial intravenous (IV) infusion followed by a second

infusion 2 weeks later and a subsequent infusion 6 months after the first treatment (Figure 2A). The first and third infusion will be considered in defining inebilizumab treatment patterns.

Treatment duration will be the sum of days under inebilizumab exposure during the follow-up. Number of days under exposure will be calculated for the first and the third infusion as the difference between end date of inebilizumab exposure period and the administration/prescription/dispensation date (Figure 2B).

[figure not shown]
Inebilizumab complete **exposure period** will be assumed to last 180 days after drug administration/prescription/dispensation. The **end date of the exposure** period will be defined as the end of each inebilizumab exposure period within follow-up or the end date of follow-up if comes first (Figure 2B).

A patient will be considered to be in inebilizumab **continuous use** if no gap longer than 60 days occurs between the end date of the first inebilizumab exposure period and the beginning of the third (2B). **Temporary discontinuation** (intermittent users) will be defined in patients with gaps between inebilizumab exposure periods longer than 60 days but with a subsequent inebilizumab administration/prescription/dispensation during the follow-up. A patient will be defined as having **permanently discontinued** inebilizumab if no subsequent inebilizumab treatment is registered during the follow-up after the end date of the first inebilizumab exposure period.

Switchers will be a subgroup of patients who discontinue inebilizumab (temporarily or permanently) during the follow-up and have other NMOSD maintenance drug administered/ prescribed (Table 9) after the end date of inebilizumab exposure period (2C). The alternative NMOSD drugs will be described.

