6.7.2 Planned Analyses

An eligible population will include all inebilizumab users identified during the study period in the selected data sources. From the eligible population, the population for analysis will be created by applying the study inclusion criteria, as defined in [section 6.2.1](#). The number and proportion of patients not included in the study for specific reasons will be presented in a STrengthening the Reporting of OBServational studies in Epidemiology (STROBE) (37) diagram.

All analyses will be conducted for the overall study population and in sub-groups of special interest: patients concomitantly receiving other immunosuppressive agents ([Table 9](#) and [Table 10](#) in Annex 3), and patients aged >65 years at the index date, if the sample size permits. Further details for the sample size required to conduct each of the analysis will be provided in the SAP.

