6.7.2.2 Objective 2: Treatment patterns of inebilizumab

The number and proportion of patients in the overall study population receiving the drug, and by dose stratification, (below or above the recommended dose in the product characteristics [300 mg/IV infusion]) will be reported at each of the first, second, and third infusion. Additionally, the number and proportion of patients who change dose between the individual infusions as well as the time (in days) between the first and each subsequent treatment (regardless of dose) will be reported.

Inebilizumab treatment patterns, as described below, will be assessed in the period of 12 months from index date and only patients with a complete 12-month follow-up, regardless of inebilizumab discontinuation, will be considered.

The number and proportion of patients who experience the following treatment pattern related events will be reported separately for each of the events: continuous and discontinuous treatment, switching, use of add-on therapies, according to what is defined in [section 6.3.3](#). For all the events, the denominator consists of all patients exposed to inebilizumab and followed for the full 12-month period.

The median time to switching and the median time to use of add-on drugs will be described in the subgroups of switchers and patients using add-on therapies (as defined in [section 6.3.3](#)), respectively. For the subgroup of switchers (as defined in [section 6.3.3](#)), the time to switch will be calculated as the time from the index date until the first recorded start date of another NMOSD maintenance drug. For the subgroup of patients using add-on therapies (as defined in [section 6.3.3](#)), the time to add-on drug use will be calculated as the time from the index date until the first recorded start date of an add-on drug.

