6.9 Limitations of Research Methods

Automated healthcare databases are appropriate for real-world studies due to the recording of prescriptions and clinical data from routine clinical practice, independently of any study purposes.

The use of secondary data allows the identification of all drug users which limits selection bias, since all patients fulfilling the inclusion criteria are included in the study. Inebilizumab is available in secondary care settings (hospitals and specialized centers) which narrows down the area of searching for eligible patients. This is particularly relevant to answer the research objectives due to the fact NMOSD is a rare condition and inebilizumab is expected to be used by a small number of individuals. Furthermore, the

inclusion of several countries contributes to the representativeness of European inebilizumab users.

However, some limitations should be addressed:

- Inebilizumab is a novel drug, so one can expect changes over time in clinical practice regarding the use of the drug. The uptake of inebilizumab in the population covered by the data sources may be slow at the beginning of the study period and is likely to increase closer to the end. This pattern may result in a small sample of patients with complete follow-up, i.e., eligible to answer objectives 2 and 3. Thus, treatment patterns and safety outcomes may lack precision. Additionally, long-term treatment patterns and safety outcomes will not be assessed in this study.
- Despite the anticipated high reliability and validity of the data sources proposed for the study, there may be a potential of under- or misreporting of diagnostic information. In addition to variation in ICD-10 coding practices across countries, NMOSD is a rare and complex condition, with wide extent of the diagnostic work-up and diverse diseases can mimic NMOSD (39), making a late diagnosis or potential misclassification more probable. NMOSD-associated conditions may also be prone to misclassification, particularly the less severe ones, which may underestimate their frequency.
- Data collected for administrative purposes may be incomplete for medical information not directly related to reimbursement. This can affect the measurement of variables to characterize inebilizumab users and safety outcomes, underestimating its frequency. When available, the use of disease registries may minimize this limitation.

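### Objective 2 is set for the overall study population, but continuation, discontinuation, switching, add-on use and duration are analysed only in patients followed for a full 12 months

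*Protocol*

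**What the plan says.** Section 5 words the second objective as "To describe inebilizumab treatment patterns in the overall study population and sub-groups of special interest in the first 12 months after starting treatment". Section 6.7.2 adds that "All analyses will be conducted for the overall study population and in sub-groups of special interest".

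The analysis set is narrower. Section 6.3.3 states that "only those with complete 12-month follow-up will be considered in the evaluation of the treatment patterns", in a passage that also covers treatment duration. Section 6.7.2.2 repeats that "only patients with a complete 12-month follow-up, regardless of inebilizumab discontinuation, will be considered", and for continuous and discontinuous treatment, switching and add-on use "the denominator consists of all patients exposed to inebilizumab and followed for the full 12-month period". The abstract has the same restriction.

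In Section 6.1, follow-up stops at 12 months, death, disenrolment or the end of the study period, whichever is first. Entry has no earlier cut-off: "Patients initiating the treatment will be identified throughout the study period".

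Section 6.9 expects uptake to grow towards the end of the study period and practice to change over time. The consequence it draws is one of numbers: "This pattern may result in a small sample of patients with complete follow-up".

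Dose at each of the first three infusions is the exception. Section 6.7.2.2 reports it for the overall study population.

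**The concern.** The completer rule conditions on something that happens after treatment starts: surviving and staying registered for a year. Section 6.2 limits the cohort to first-time users partly to avoid survivor and follow-up bias, and the completer rule lets both back in for this objective. Section 6.9 also argues that selection bias is limited because every patient meeting the inclusion criteria is in the study. That does not hold for the objective-2 proportions.

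Two groups are lost:

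- **Patients who die or disenrol within the year.** Their exit may be related to how treatment went, so leaving them out can bias the proportions.
- **Patients who start in the last 12 months.** Their loss is administrative. It costs numbers, and it tilts the sample towards earlier starters in a setting where the protocol expects practice to change.

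Add-on use can occur from day 0, so both groups may have add-on events that are observed and then discarded. The same protocol keeps all initiators, with censoring, for the AESI incidence rate and time to onset (Section 6.7.2.3).

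**Working it through.** **1. The plan's own precision figure.** Section 6.5 uses n = 1.96² × p(1 − p)/d². For p = 1%, d = 1%: 3.8415 × 0.0099/0.0001 = 380 (Table 3: 380). For p = 4%, d = 2%: 3.8415 × 0.0384/0.0004 = 369 (Table 3: 369). A cohort of 400 gives half-widths of 0.98 points at 1%, 1.92 at 4% and 3.92 at 20%.

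**2. Starters who cannot reach 12 months.** T is the study period in months from Table 1. The uptake shape is assumed, since the protocol gives none beyond expecting a slow start and a later increase.

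| Source | T | Flat: 12/T | Linear rise from zero: 1 − ((T − 12)/T)² |
|---|---|---|---|
| France | 57 | 21% | 38% |
| Germany | 54 | 22% | 39% |
| Italy | 56 | 21% | 38% |
| Netherlands | 41 | 29% | 50% |
| Spain | 53 | 23% | 40% |
| Pooled (Table 4 adult populations as weights, assumed) | | 21.8% | 38.9% |

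Counted inclusively, the French and German dates in Table 1 give 56 and 53 months rather than 57 and 54. This moves the shares by less than one point.

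**3. What is left of 400 before any death or disenrolment.** Flat: 400 × (1 − 0.218) ≈ 313. Rising: 400 × (1 − 0.389) ≈ 245. The half-width at 20% goes from 3.9 to 4.4 or 5.0 points. At 4% it becomes 2.2 or 2.5, and at 1% it becomes 1.1 or 1.2, so the precision quoted for 400 does not carry over to these proportions.

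**4. When each event can first occur (Section 6.3.3).**

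- Add-on use: during any exposure period, so from day 0.
- Discontinuation and switching: only after an exposure period ends, so not before day 180.
- The gap rule: resolved at about day 180 + 60 = 240.

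A patient censored before day 180 therefore carries no information on discontinuation or switching. Steps 2 and 3 repeated with 240 days (7.9 months) and 180 days (5.9 months) in place of 12 months give the most an all-starter analysis can use for these two outcomes:

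| Uptake | Completers | Observed to day 240 | Observed to day 180 | Half-width at 20%, completers → all starters |
|---|---|---|---|---|
| Flat | 313 | 343 | 357 | 4.4 → about 4.2 |
| Rising | 245 | 293 | 319 | 5.0 → 4.4 to 4.6 |

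For add-on use, all 400 contribute for as long as they are observed.

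**5. Can a bias be computed?** Only with inputs the protocol does not give. Two illustrations:

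- *Calendar trend.* Assume 12-month discontinuation falls from 30% to 15% over 56 months with linearly rising uptake. The mean start is at two-thirds of the window. All starters: 30 − 15 × (2/3) = 20.0%. Completers (starts up to month 44): 30 − 15 × 29.3/56 = 22.1%. Patients observed to day 180 or day 240: 21.1% or 21.4%.
- *Leavers.* Assume 5% leave, half of them after the event, against 10% of completers with the event. All starters: 0.95 × 10 + 0.05 × 50 = 12.0%. Completers: 10%.

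The first overstates and the second understates.

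**The case against.** **The rule is open and consistent.** The abstract and Sections 6.3.3 and 6.7.2.2 all state it, and Section 6.9 discloses its cost in numbers. In Sections 5 and 6.7.2, the overall study population is paired with the sub-groups and could mean no more than that the analysis is not confined to them. This is fair as a reading. It does not remove the selection, which Section 6.9 never names.

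**The definitions partly require it.** Separating temporary from permanent discontinuation needs the whole window, and neither discontinuation nor switching exists before day 180. The comparison with AESI, which are dated events countable from day 0, is therefore imperfect. This stands: a 3-month estimate of discontinuation or switching would be zero by definition, and step 4 shows a modest gain in precision for these two outcomes. It does not cover add-on use.

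**The fix does not cure a calendar trend.** This also stands. In the step 5 example, half to two-thirds of the 2.1-point excess remains.

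**Losses may be small in the largest source.** Section 6.4.1 gives SNDS 99% population coverage, with exit by death, emigration or end of insurance. This is plausible, but the protocol gives no attrition figure for any source.

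**Stronger readings that the document does not support.** A reader might infer that objective 2 goes unanswered as a whole. It does not: dose by infusion is reported for all starters, and patients who stop the drug but remain observable are kept. A reader might also infer that the estimates are biased by a known amount or in a known direction. The illustrations rest on assumed inputs and point opposite ways.

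**Conclusion.** The point holds in full for add-on use and in smaller form for discontinuation, switching and duration. As fixed in the protocol, these results describe initiators who stayed observable for a year and who lean towards earlier starts, which is not the population named in the objective.

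The only size that can be derived is the share of late starters excluded: about 22% with flat uptake and 39% with linearly rising uptake. Both use the Table 1 durations and Table 4 population weights. Deaths and disenrolments add to this by an amount the document does not allow one to estimate. The bias itself cannot be quantified or signed from the document.

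The change should be made: it is cheap, and the study already plans censored analyses in all initiators for another objective. It does not put the study as a whole in doubt.

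**What to change.** 1. In Sections 6.3.3 and 6.7.2.2, estimate the cumulative incidence of first add-on use (from day 0), first discontinuation and first switch in all new users. Use the Aalen-Johansen estimator, with death as a competing event and censoring at disenrolment or end of study period.
2. Give discontinuation a dated event consistent with the existing 180-day exposure period and 60-day gap. Report discontinuation and switching only at time points after day 180, for example 9 and 12 months, and not at 3 months.
3. Keep the completer proportions as a secondary table for the temporary and permanent labels. Report the numbers excluded from it by reason: death, disenrolment, or start less than 12 months before the end of the study period.
4. In Section 6.9, say that the completer table reflects patients who stayed observable for 12 months and leans towards earlier starters. Say also that end-of-study censoring removes only part of any calendar-time difference.

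The cost is protocol and SAP wording, one more standard analysis per data source on data already extracted, and two tables instead of one.

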The use of **add-on therapies** will be identified by administration/prescription/dispensation of other NMOSD maintenance or other immunosuppressive drug(s) (Table 9 and Table 10) during any of inebilizumab exposure period (2D). Corticosteroid pre-medication before inebilizumab infusion (used to reduce potential infusion reactions) will not be considered as an add-on therapy.

Figure 2 Inebilizumab treatment patterns

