	6A551Z3 - Pheresis of Plasma, Multiple	ICD-10-PCS
	8-820 Therapeutic plasmapheresis	OPS

Abbreviations: ATC, Anatomical therapeutic chemical; ICD-10: 10th Revision of International Classification of Diseases; OPS, operation and procedure classification system, PCS, Procedure Coding System

* Only intravenous administrations

Table 9 NMOSD Maintenance Therapies

Name of Agent	Description	Coding
1. Oral Steroids	H02 - Corticosteroids for systemic use	ATC
2. Immunosuppressive therapies		
a. Azathioprine	L04AX01	ATC
b. Mitoxantrone	L01DB07	ATC
c. Mycophenolate Mofetil	L04AA06	ATC
d. Methotrexate	L01BA01; L04AX03	ATC
e. Cyclophosphamide	L01AA01	ATC
3. B-Cell Targeting Therapy (anti-CD20)		
a. Ocrelizumab	L04AA36 /L04AG08 from 2024	ATC
	6-00a.e Atezolizumab, parenteral	OPS
b. Ofatumumab	L04AA52/ L04AG12 from 2024	ATC
	6-006.4 Ofatumumab, parenteral	OPS
c. Rituximab	L01FA01	ATC
	6-001.h Rituximab, intravenously	OPS
	6-001.j Rituximab, subcutaneous	
4. Tocilizumab	L04AC07	ATC
	6-005.m Tocilizumab, intravenously	OPS
	6-005.n 8 Tocilizumab, subcutaneous	
5. Eculizumab	L04AA25/L04AJ01 from 2024	ATC
	6-003.h Eculizumab, parenteral	OPS
6. Satralizumab	L04AC19	ATC

Abbreviations: ATC, Anatomical therapeutic chemical; NMOSD, Neuromyelitis optica spectrum disorder; OPS, operation and procedure classification system

Table 10 Other Immunosuppressive Drugs of Interest

Name of Agent	Description	Coding
1. Interferon beta-1a and 1b	L03AB07; L03AB08	ATC
2. Dimethyl-fumarate	L04AX07; L04AX09	ATC
3. Alemtuzumab	L04AA34/L04AG06 from 2024	ATC
	6-001.0 Alemtuzumab, parenteral	OPS
4. Fingolimod	L04AA27/L04AE01 from 2024	ATC
5. Natalizumab	L04AA23/L04AG03 from 2024	ATC
	6-003.f Natalizumab, parenteral	OPS
6. Glatiramer acetate	L03AX13	ATC
7. Peginterferon beta-1a	L03AB13	ATC
8. Teriflunomide	L04AA31/L04AK02 from 2024	ATC
9. Bortezomib	L01XG01	ATC
	6-001.9 Bortezomib, parenteral	OPS
10. Cladribine	L01BB04; L04AA40	ATC
	6-00a.4 Cladribine, oral	OPS
11. Daclizumab	L04AC0	ATC
	6-009.9 Daclizumab, parenteral	OPS
12. Ozanimod	L04AA38/L04AE02 from 2024	ATC
13. Siponimod	L04AA42/L04AE03 from 2024	ATC
14. Tacrolimus	L04AD02	ATC

Abbreviations: ATC, Anatomical therapeutic chemical; OPS: operation and procedure classification system

Table 11 Pain Medication

Name of Agent	Description	Coding
1. Anti-inflammatory and antirheumatic drugs	M01	ATC
2. Topical products for joint and muscular pain	M02	ATC
3. Muscle relaxants	M03	ATC
4. Anesthetic drugs	N01	ATC
5. Analgesics	N02	ATC

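### Section 6.7.2.2 does not require the record that ends the time-to-switch clock to follow the end of inebilizumab exposure, so switchers who also started a maintenance drug during exposure are timed to the add-on date

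*Protocol*

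**What the plan says.** Three rules meet here.

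- **Who is a switcher (section 6.3.3).** Patients who discontinue inebilizumab, temporarily or permanently, and "have other NMOSD maintenance drug administered/ prescribed (Table 9) after the end date of inebilizumab exposure period". A complete exposure period "will be assumed to last 180 days after drug administration/prescription/dispensation".
- **What an add-on is (section 6.3.3).** A record of "other NMOSD maintenance or other immunosuppressive drug(s) (Table 9 and Table 10) during any of inebilizumab exposure period". Table 9 therefore serves both definitions, and timing relative to exposure separates them. Table 9 in Annex 3 opens with "1. Oral Steroids", coded "H02 - Corticosteroids for systemic use", and also lists azathioprine, mycophenolate mofetil and rituximab.
- **How the times are measured (section 6.7.2.2).** For switchers, the time is "calculated as the time from the index date until the first recorded start date of another NMOSD maintenance drug". For add-on users, "the time to add-on drug use will be calculated as the time from the index date until the first recorded start date of an add-on".

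The median time to switching is a named output in the Abstract and in section 6.7.2.2. Treatment patterns are assessed over the 12 months from index, in patients with complete follow-up.

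**The concern.** The event that defines a switcher and the record that ends the switcher's clock are described differently. Section 6.3.3 needs a Table 9 record after exposure ends. Section 6.7.2.2 takes the first Table 9 start counted from index and sets no lower limit at the end of exposure. Its cross-reference to section 6.3.3 is attached to the subgroup, so it settles who is counted but not which record is used.

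Where a switcher also started a Table 9 drug during exposure, the literal rule reports that add-on start as the switch. The median time to switching then mixes add-on dates with real switches and is too short.

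The overlap is foreseeable because one drug list serves both definitions, that list includes oral steroids, and users of concomitant immunosuppressants are a planned subgroup for all analyses (section 6.7.2). The exemption for corticosteroid pre-medication in section 6.3.3 is stated for add-on therapy only.

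**Working it through.** The protocol gives no figure for time to switch, so there is nothing to reproduce. The check sets the definitions on one day scale and then illustrates the size.

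**Step 1: earliest admissible switch.** Index is day 0 and the first exposure period ends on day 180 (section 6.3.3). A qualifying Table 9 record must come after that, so the earliest switch is day 181. Follow-up ends at about day 365.

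**Step 2: a worked patient** (hypothetical dates, drugs from Table 9). Inebilizumab starts on day 0; azathioprine is first recorded on day 30; exposure ends on day 180; no further inebilizumab is given; rituximab is recorded on day 250.

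| Rule | Record used | Days from index |
|---|---|---|
| Switcher definition, 6.3.3 | rituximab | 250 |
| Time to switch as written, 6.7.2.2 | azathioprine | 30 |
| Time to add-on, 6.7.2.2 | azathioprine | 30 |

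The literal switch time is 250 − 30 = 220 days too short, falls 180 − 30 = 150 days before exposure ends, and equals the time to add-on. Without the azathioprine record both switch rules would give 250.

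**Step 3: effect on the median.** The following are assumptions, not document figures: qualifying switch days are uniform on the 185 days from 181 to 365, and a fraction q of switchers also has a Table 9 start uniform on days 1 to 180. On the literal rule those patients take the earlier date. For q below 50% the median is

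median = 180 + 185 × (0.5 − q) / (1 − q), rounded up to a whole day.

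| q | Calculation | Literal median (days) | Shift from 273 |
|---|---|---|---|
| 0% | 180 + 185 × 0.500 = 272.5 | 273 | 0 |
| 10% | 180 + 185 × 0.444 = 262.2 | 263 | −10 |
| 20% | 180 + 185 × 0.375 = 249.4 | 250 | −23 |
| 30% | 180 + 185 × 0.286 = 232.9 | 233 | −40 |
| 50% | half of all times are at or below 180 | 180 | −93 |

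A simulation of 200,000 switchers under the same assumptions gave 273, 263 and 180 for q = 0%, 10% and 50%. The share of switchers with a time of 180 days or less, which section 6.3.3 rules out, equals q.

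**Step 4: with the clock tied to the qualifying record.** No time can be 180 days or less, and under the same assumptions the median is 273 whatever the value of q.

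**The case against.** The strongest reply is that this is only a qualifier left unrepeated. The sentence opens with switchers as defined in section 6.3.3, the quantity is called time to switch, add-ons are timed separately, and the literal reading lets one record serve as both add-on and switch. The authors very probably meant the qualifying drug. That stands as a view of intent, but the sentence does not say so. Its neighbour ends the add-on clock at a defined add-on drug, whereas the switching sentence names only the general class of maintenance drugs.

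A second reply is that section 6.7.1 leaves full variable definitions to the SAP. But the protocol does not defer this rule; it states the calculation, and an SAP that used the qualifying record would depart from that wording. Figure 2C, cited for switching, is not reproduced in the text available for this review. If it marks the switch date it would support the intended reading, but the sentence would still need correcting.

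Three stronger readings might be inferred and are not supported:

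- **Negative times from drugs started before index.** Section 6.7.2.2 confines the assessment to the 12 months from index, so an earlier start lies outside the window. The clear problem cases are drugs newly started during exposure. How repeat records of a continuing drug count is not stated.
- **All switchers mistimed.** A switcher whose first Table 9 start falls after exposure gets the right time.
- **A large bias shown.** Neither q nor the uniform dates come from the documents, and at q = 10% the shift is only 10 days.

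**Conclusion.** The point holds in a limited form. Applied literally, section 6.7.2.2 gives switchers who also started a Table 9 drug during exposure a switch time that section 6.3.3 makes impossible, and it biases the median time to switching downward. The size cannot be fixed from the documents. Under the stated assumptions the shift runs from 10 days at 10% overlap to 93 days at 50%; the direction does not depend on those assumptions. The share would be expected to be highest in the concomitant-immunosuppressant subgroup.

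The consequence is confined to one named descriptive output. The proportion of switchers, the other treatment-pattern proportions and all AESI estimates are untouched, and no hypothesis test is involved. It merits correction because the rule as stated gives a wrong number and the remedy is a single sentence.

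**What to change.** In section 6.7.2.2, define time to switch as the number of days from the index date to the first Table 9 record dated after the end date of the inebilizumab exposure period that precedes the discontinuation, that is, the record that makes the patient a switcher under section 6.3.3. Carry the same wording into the SAP.

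The cost is one sentence. It needs no new data, since the exposure end date and the Table 9 records are already required to classify switchers.
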